2.3.4 Evaluation of response

Response criteria for patients enrolled onto the study will follow the guidelines recommended by the 1999 International Workshop on Response Criteria for NHL. (Cheson et al. 1999) All responses will be characterized as either complete remission (CR), unconfirmed complete remission (CRu), partial remission (PR), stable disease (SD), or progression of disease (POD). Response will be assessed after every three cycles of combination therapy. Response will be assessed every 4 months thereafter while the patient receives obinutuzumab maintenance treatment.

3. STUDY POPULATION

3.1 INCLUSION CRITERIA

Patients must meet the following criteria for study entry:

- A diagnosis of small lymphocytic lymphoma, follicular lymphoma (grades 1-3a), or marginal zone lymphoma.
- Evidence of progression or lack of response following at least 1 prior treatment for indolent lymphoma.
- Able and willing to provide written informed consent and to comply with the study protocol
- Age ≥ 18 years
- Must have at least 1 node greater than 1.5cm in short axis diameter
- Adequate hematologic function (unless abnormalities are related to NHL), defined as follows:
 - Hemoglobin ≥ 9.0 g/dL
 - Absolute neutrophil count $\geq 1.5 \times 10^9$ /L
 - Platelet count $\geq 75 \times 10^9$ /L
 - ANC $< 1.5 \times 10^9$ /L or PLT count less than 100×10^9 /L if cytopenia is due to extensive bone marrow involvement of disease as determined by the treating physician.
- For men who are not surgically sterile, agreement to use a barrier method of contraception for ≥ 6 months after the last obinutuzumab dose. In addition, male patients must agree to request that their partners use an additional method of contraception, such as oral contraceptives, intrauterine device, barrier method of contraception or spermicidal jelly

- For women of reproductive potential who are not surgically sterile, agreement to use two adequate methods of contraception, such as oral contraceptives, intrauterine device, or barrier method of contraception in conjunction with spermicidal jelly for ≥ 18 months after the last obinutuzumab dose.
- Females of childbearing potential (FCBP)† must have a negative serum pregnancy test with a sensitivity of at least 50 mIU/mL within 10 – 14 days prior to and again within 24 hours of prescribing lenalidomide and must either commit to continued abstinence from heterosexual intercourse or begin TWO acceptable methods of birth control, one highly effective method and one additional effective method AT THE SAME TIME, at least 4 weeks before she starts taking lenalidomide. FCBP must also agree to ongoing pregnancy testing. Men must agree to use a latex condom during sexual contact with a female of child bearing potential even if they have had a successful vasectomy.
- All study participants must be registered into the mandatory Revlimid REMS® program, and be willing and able to comply with the requirements of Revlimid REMS® program.

For patients with bulky disease (tumors >5 cm); must be able to take aspirin (81mg or 325 mg) daily as prophylactic anticoagulation (patients intolerant to ASA may use warfarin or low molecular weight heparin).

- Females of reproductive potential must adhere to the scheduled pregnancy testing as required in the Revlimid REMS® program. Able to take aspirin (81 or 325 mg) daily as prophylactic anticoagulation (patients intolerant to ASA may use warfarin or low molecular weight heparin).

† A female of childbearing potential is a sexually mature woman who: 1) has not undergone a hysterectomy or bilateral oophorectomy; or 2) has not been naturally postmenopausal for at least 24 consecutive months (i.e., has had menses at any time in the preceding 24 consecutive months).

3.2 EXCLUSION CRITERIA

- Evidence ongoing transformation into aggressive NHL.
- History of severe allergic or anaphylactic reactions to monoclonal antibody therapy
- Known hypersensitivity to thalidomide or lenalidomide.
- Regular treatment with corticosteroids during the 4 weeks prior to the start of Cycle 1, unless administered for indications other than NHL at a dose equivalent to ≤ 30 mg/day prednisone

- History of prior malignancy within the last 5 years, with the exception of curatively treated basal or squamous cell carcinoma of the skin and low-grade in situ carcinoma of the cervix
- Evidence or history of significant, uncontrolled concomitant diseases that could affect compliance with the protocol or interpretation of results, including significant cardiovascular disease (such as New York Heart Association Class III or IV cardiac disease, severe arrhythmia, myocardial infarction within the previous 6 months, unstable arrhythmias, or unstable angina) or pulmonary disease (including obstructive pulmonary disease and history of bronchospasm)
- Known active bacterial, viral, fungal, mycobacterial, parasitic, or other infection (excluding fungal infections of nail beds) or any major episode of infection requiring treatment with IV antibiotics or hospitalization (relating to the completion of the course of antibiotics, except if for tumor fever) within 4 weeks prior to the start of Cycle 1

Patients with suspected active or latent tuberculosis (latent tuberculosis needs to be confirmed by positive Interferon-gamma release assay)

- Vaccination with live vaccines within 28 days prior to start of treatment
- Any of the following abnormal laboratory values (unless any of these abnormalities are due to underlying lymphoma):

Creatinine > 1.5 times the upper limit of normal (ULN) (unless creatinine clearance normal), or calculated creatinine clearance < 40 mL/min (using Cockcroft–Gault formula; see Appendix D)

AST or ALT $> 2.5 \times$ ULN

Total bilirubin $> 1.5 \times$ ULN (or $> 3 \times$ ULN for patients with documented Gilbert syndrome)

Any history of hepatitis B infection.

- Positive test results for hepatitis C (hepatitis C virus [HCV] antibody serology testing)

Patients positive for HCV antibody are eligible only if PCR is negative for HCV RNA

- Known history of HIV seropositive status
- Positive test results for human T-lymphotropic 1 (HTLV 1) virus

HTLV testing is required in patients from endemic countries (Japan, countries in the Caribbean basin, South America, Central America, sub-Saharan Africa, and Melanesia)

- Pregnant or lactating
- ECOG performance status greater than 2.
- Participation in another clinical trial with drug intervention within 21 days prior to start of Cycle 1 and during the study
- Patients with SLL/CLL will be excluded during the phase I portion of the study

3.3 IMMUNIZATION DURING B-CELL DEPLETION

To date, no vaccination studies have been performed with obinutuzumab. No vaccination with live virus vaccines should be given to patients treated with obinutuzumab.

4. TREATMENT PLAN

4.1 Phase I

Three dose levels of lenalidomide (10 mg, 15 mg, 20 mg) will be evaluated with a fixed dose of obinutuzumab (1000mg) as outlined in Table 1. (obinutuzumab will be given in divided doses on cycle 1; 100mg IV on day 1, and 900mg IV on day 2, subsequent doses will be given over 1 day) Up to 18 patients may participate in the Phase I component of the study, depending on the level at which toxicity is observed. Subjects will be assigned to a dose level based on the order of study entry and toxicities seen in prior patients. The dose escalation process is described below. There will be no intra-patient dose escalation. DLT will be assessed during the first course of each cohort (28 days), and refers to a medically significant event which meets criteria using National Cancer Institute Common Terminology Criteria for Adverse Events (NCI CTCAE) version 4. (see section 2.3.2)

Table 1. Dose levels to be tested in phase I portion

Dose Level	Lenalidomide Dose (days 2-22 followed by 6 days of no therapy)	Obinutuzumab dose
-1	5 mg	1000mg IV
1	10 mg	
2	15 mg	
3	20 mg	

4. 2 Phase II

Additional pts will be enrolled into two cohorts at the recommended dose level (MTD) established in Phase I up to a maximum of 30 patients each in two independently enrolling cohorts.

Cohort A: 30 patients with relapsed/refractory follicular lymphoma

Cohort B: 30 patients follicular lymphoma, marginal zone lymphoma or SLL

[figure not shown]
4. 3 Treatment Schedule

Lenalidomide capsules will be taken orally daily each day on days 2 - 22, followed by 6 days of no therapy of each 28-day cycle. Obinutuzumab will be given by intravenous infusion on day 1,,2, 8, 15, and 22 of cycle one and on day 1 of each subsequent cycle up to 6 cycles. Patients who do not progress following 6 cycles and are deriving benefit from the combination in the opinion of the treating physician can receive further cycles of combination up to 12 cycles of lenalidomide therapy. (As long as the patient does not exhibit progression, the decision of how many cycles of combination therapy beyond 6 is at the discretion of the treating team and investigator).

Extended dosing of obinutuzumab will begin after combination therapy if patients demonstrate at least stable disease on response assessment. In the extended dosing schedule, obinutuzumab will be administered every 2 months, and in the absence of progression, will be dosed for maximum of 30 months (combination + maintenance).

Patients that do not have at least a partial remission following 12 cycles of combination therapy will not continue with extended obinutuzumab treatment.

TREATMENT REGIMEN

*(GA101 will be given in divided doses on first dose in cycle 1; 100mg IV on day 1, and 900mgIV on day 2, subsequent doses will be given over 1 day)

This research study protocol allows the subject to receive up to 21 infusions of obinutuzumab. Even if the treatment is shown to be of benefit, additional infusions of obinutuzumab beyond that allowed in the protocol cannot be given to the subject while they are participating in this study.

Visit schedule and assessments

Screening Assessments and all on study scheduled visits and assessments are outlined in Table of Study Assessments. All timepoints outlined in the Schedule of Assessments allow variation of +/- 3 days.

Due to the drug delivery from an outside facility, clinicians should allow up to 72 hours from patient assessment/evaluation to the start of each cycle.

Pregnancy testing and counseling must be performed if a subject misses her period or if her pregnancy test or her menstrual bleeding is abnormal. Study drug treatment must be discontinued during this evaluation. In addition to the required pregnancy testing, the Investigator must confirm with FCBP that she is continuing to use two reliable methods of birth control at each visit.

An unscheduled visit can occur at any time during the study. Source must be maintained for these unscheduled visits. The date for the visit and any data generated must be recorded on the appropriate CRF. Source documents for these unscheduled visits must also be maintained.

At treatment discontinuation, subjects will undergo off study evaluations per the Schedule of Assessments, Section 2. In addition, a safety assessment will be done approximately 28 days post the last dose of study drug.

5. STUDY MEDICATION

5.1 OBINUTUZUMAB

Obinutuzumab is provided as a single dose, sterile liquid formulation in 50 mL pharmaceutical grade glass vials containing a nominal 1000 mg of obinutuzumab. The formulated drug product consists of 25 mg/mL drug substance (G3 material) formulated in histidine, trehalose, and poloxamer 188. The vials contain 41 mL (with 2.5% overfill). Genentech will provide obinutuzumab to investigational site as an IMP.

For further details, see the obinutuzumab Investigator's Brochure.

5.1.1 OBINUTUZUMAB DOSE AND SCHEDULE

Obinutuzumab 1000mg will be given IV on day 8, 15, and 22 of cycle one and on day 1 of each subsequent cycle up to 6 cycles during lenalidomide dosing. First dose of 1000mg will be split into day 1 and 2 of cycle 1 as outlined in section

5.1.4. If the patient attains at least stable disease, the patient will receive obinutuzumab 1000mg IV every 2 months for a maximum of 2 years. For dosing instructions, see section 6.2.

5.1.2 OBINUTUZUMAB PREPARATION

Obinutuzumab drug product intended for IV infusion is prepared by dilution of the drug product into an infusion bag containing 0.9% NaCl to the final drug concentration of 4 mg/mL. Using a 250-mL infusion bag containing 0.9% NaCl, withdraw and discard 40 mL of the NaCl. Withdraw 40 mL of obinutuzumab from a single glass vial and inject into the infusion bag (discard any unused portion of obinutuzumab left in the vial). Gently invert the infusion bag to mix the solution; do not shake.

Do not use obinutuzumab beyond the expiration date stamped on the carton.

5.1.3 OBINUTUZUMAB PRE MEDICATIONS

5.1.3.1 Obinutuzumab Pre-medications

Thirty to 60 minutes prior to all obinutuzumab infusions, the following pre-medications will be given (unless contraindicated):

- Oral acetaminophen (e.g., 650–1000 mg) AND
- An antihistamine such as diphenhydramine (50–100 mg)
- For Cycle 1, prophylactic corticosteroids (e.g., 100 mg IV prednisolone) at least one hour prior to the obinutuzumab infusion. An equivalent

dose of dexamethasone (15-20mg) or methylprednisolone (80mg) is acceptable but hydrocortisone should not be used.

In subsequent cycles, steroids should be given to patients who experienced a severe IRR with the prior infusion of obinutuzumab or who are thought to be at high risk for infusion-related reactions, as assessed by the investigator.

5.1.3.2 Tumor Lysis Syndrome Prophylaxis

Patients who are considered to have a high tumor burden and who are considered to be at risk for tumor lysis by the investigator should additionally receive tumor lysis prophylaxis prior to the initiation of treatment. These patients should be well hydrated starting 1 to 2 days before the first dose of obinutuzumab. In addition, all patients considered to have high tumor burden and who are considered to be at risk for tumor lysis should be treated with allopurinol 300 mg/day orally or a suitable alternative treatment starting 12 to 24 hours prior to treatment on Day 1 of Cycle 1. These patients should continue to receive repeated prophylaxis with allopurinol and adequate hydration prior to each subsequent infusion, if deemed appropriate by the investigator

5.1.4 OBINUTUZUMAB ADMINISTRATION

First Infusions

- First dose of obinutuzumab will be split into two days on cycle 1. Day 1 patient will receive 100mg, day 2 patient will receive 900mg. During cycle 1, rate on day 1 will be 25mg/hr over 4 hours (25ml/hr at 1mg:1ml dilution).
- In the absence of IRRs/hypersensitivity, the rate of the infusion on cycle 1 day 2 will be escalated in increments of 50 mg/hr (14ml/hr) every 30 minutes to a maximum rate of 400 mg/hr(100ml/hr).
- The patient will receive 1000mg of obinutuzumab for the remainder of the cycle 1 infusions (day 8, 15, 22) at the initial rate of 50 mg/hr (12.5 ml/hr) and increased by 50 mg/hr (12.5 ml/hr) increments at 30 minute intervals, as tolerated, to a maximum rate of 400 mg/hr (100 ml/hr).
- If a hypersensitivity or IRR develops, the infusion should be temporarily interrupted or slowed down and concomitant medication may be administered if deemed appropriate by the investigator.
- Upon the resolution of symptoms, the infusion will resume at one-half the previous rate (the rate being used at the time that the hypersensitivity or IRR occurred) and infusion-rate escalation may resume at the increments and intervals described above. If patient does not demonstrate signs of acute infusion reaction (hypotension or shortness of breath), the patient can have IV

discontinued prior to 1 hour on second infusion and beyond.

Second cycle and Subsequent Infusions

- If a patient's previous obinutuzumab infusion(s) in cycle 1
- were well tolerated (defined by an absence of Grade ≥ 2 IRRs during a final infusion rate of ≥ 100 mg/hr (25cc/hr in standard 4mg:1ml dilution), subsequent infusions beginning with cycle 2 will be administered at an initial rate of 100 mg/hr (25ml/hr) and increased by 100-mg/hr (25ml/hr) increments at 30-minute intervals, as tolerated, to a maximum rate of 400 mg/hr (100ml/hr).
- If a hypersensitivity or IRR develops, the infusion should be temporarily interrupted or slowed down and concomitant medication may be administered if deemed appropriate by the investigator.
- Upon the resolution of symptoms, the infusion will resume at one-half the previous rate (the rate being used at the time that the hypersensitivity or infusion-related reaction occurred) and infusion-rate escalation may resume at the increments and intervals described above.

If the previous infusion rate was not well tolerated, as defined above, instructions for the first cycle infusion rate will be used.

Table 2

After the end of the first infusion, the IV line or central venous catheter should remain in place for greater than or equal to 1 hour to be able to administer IV drugs if necessary. If no adverse events occur after 2 hours, the IV line may be removed or the central venous catheter may be de accessed. For subsequent infusions, the IV line or central venous catheter should remain in place for at least 1 hour after the end of the infusion. If no adverse events occur after 1 hour, the IV line may be removed or the central venous catheter may be de accessed.

5.1.5 OBINUTUZUMAB STORAGE

Obinutuzumab drug product should be stored at 2°C–8°C and protected from light. For the diluted product, chemical and physical in-use stability have been demonstrated at concentrations of 0.2mg/ml-20mg/mL for 24 hours at 2°C–8°C and at ambient temperature and ambient room lighting. The product should be used immediately. If not used immediately, in-use storage times and conditions prior to use are the responsibility of the user and would normally not be longer than 24 hours at 2°C–8°C. Obinutuzumab should not be frozen or shaken. Mix gently. All transfer procedures require strict adherence to aseptic techniques.

For further details, see the obinutuzumab Investigator's Brochure.

5.1.6 OBINUTUZUMAB UNUSED OR EXPIRED DRUG

All unused or expired investigational drug will be destroyed in accordance with institutional policies. Drug accountability records will be emailed to [contact] at study closure.

5.2 LENALIDOMIDE

Lenalidomide is available in 2.5 mg, 5mg and 25 mg capsule strengths for oral administration. Each capsule contains lenalidomide as the active ingredient and the following inactive ingredients: lactose anhydrous, microcrystalline cellulose, croscarmellose sodium, and magnesium stearate. The 5 mg capsule shell

5.2.1 Lenalidomide Dose and Schedule

Phase I: In the phase I portion of the study the planned dose of lenalidomide for patients with follicular lymphoma and marginal zone lymphoma (SLL patients not included in phase I portion of study) will be based upon the dose escalation table. (table 1) Patients will receive an oral dose daily on days 2 – 22 followed by 6 days rest (28 day cycle).

Table 3. Dose levels to be tested in phase I portion		
Dose Level	Lenalidomide Dose (days 2-22 followed by 6 days of no therapy)	Obinutuzumab dose
-1	5 mg	1000mg IV
1	10 mg	
2	15 mg	
3	20 mg	

Phase II: Lenalidomide will be administered orally at the maximum tolerated dose (MTD) (as defined by the Phase I portion of the study) on days 2 to 22 of a 28 day cycle in patients with follicular lymphoma and marginal zone lymphoma. Patients with a diagnosis of small lymphocytic lymphoma (SLL) will begin cycle #1 at a maximum dose of 10 mg total daily on days 2 to 22 of a 28 day cycle. This dose will be escalated by 5mg with each cycle up to the MTD if no toxicity is encountered. (see dose modification for lenalidomide table). In the absence of progression or toxicity, patients will remain on lenalidomide treatment for a total of 6-12 months/cycles.

Only one cycle of study drug will be supplied to the patient each cycle.

If a dose of lenalidomide is missed, it should be taken as soon as possible on the same day. If it is missed for the entire day, it should not be made up.

Patients who take more than the prescribed dose of lenalidomide should be instructed to seek emergency medical care if needed and contact study staff immediately. Subjects experiencing adverse events may need study treatment modifications. See Tables 6 and 7.

Supplier

Celgene Corporation will supply Revlimid® (lenalidomide) to study participants at no charge through the Revlimid REMS® program. All physicians who prescribe lenalidomide for research subjects enrolled into this trial and all research subjects enrolled into this trial must be registered in and must comply with all requirements of Celgene's Revlimid REMS® program.

Dosage form

Lenalidomide will be supplied as capsules for oral administration. The capsules are available in 2.5 mg, 5mg and 25mg capsule strengths.

Packaging

Lenalidomide will be shipped directly to the patient. Bottles will contain a sufficient number of capsules for one cycle of dosing.

Storage

Lenalidomide should be stored at room temperature away from direct sunlight and protected from excessive heat and cold.

Unused or Expired Drug

All unused or expired investigational drug will be destroyed in accordance with institutional policies. Drug accountability records will be emailed to [contact] at study closure.

Lenalidomide Prescribing Information

Lenalidomide (Revlimid®) will be provided to research subjects for the duration of their participation in this trial at no charge to them or their insurance providers. Lenalidomide will be provided in accordance with the Revlimid REMS® program. Per standard Revlimid REMS® program requirements all physicians who prescribe lenalidomide for research subjects enrolled into this trial, and all research subjects enrolled into this trial, must be registered in and must comply with all requirements of Celgene's Revlimid REMS® program. Prescriptions must be filled within 7 days. **Only enough lenalidomide for one cycle of therapy will be supplied to the patient each cycle.**

Special Handling Instructions

Women of childbearing potential should not handle or administer the clinical dosage forms unless they are wearing gloves.

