6.2 DOSE MODIFICATION: LENALIDOMIDE

Subjects will be evaluated for AEs at each visit with the NCI CTCAE v4.0, see below for full instruction on initiation of a new cycle of therapy and dose modifications during a cycle of therapy.

Table 6, 7 Lenalidomide dose adjustment steps

Table 6: LENALIDOMIDE Dose Adjustment Steps	
Starting Dose	MTD mg daily for 21 days every 28 days
Dose Level -1	MTD -5 mg daily for 21 days every 28 days
Dose Level -2	MTD -10 mg daily for 21 days every 28 days
Dose Level -3	MTD-15 mg daily for 21 days every 28 days

Table 7: LENALIDOMIDE Dose Adjustment Steps in SLL	
Starting Dose	MTD or max of 10 mg daily for 21 days every 28 days
Dose level +1	Starting dose +5 mg daily for 21 days every 28 days
Dose level +2	Starting dose +10mg daily for 21 days every 28 days
Dose level +3	Starting dose +15mg daily for 21 days every 28 days
Dose level -1	Starting dose -5 mg daily for 21 days every 28 days
Dose level -2	Starting dose -10 mg daily for 21 days every 28 days
Dose level -3	Starting dose -15mg daily for 21 days every 28 days

The minimum dose level is 15mg below MTD or 5mg daily for 21 days, (whichever is higher).

Patients who cannot tolerate or require dose reduction below 5mg daily lenalidomide will not receive further doses of lenalidomide.

If the patient is attaining clinical benefit in the opinion of the treating physician, and has attained at least a partial response, obinutuzumab dosing will continue per study design to a maximum of 21 doses.

The starting dose will be predefined during the phase I portion of the study based upon cohort (see Table 2). In the phase II portion of the study, the starting dose will be the maximum tolerated dose as defined by phase I portion.

6.2.1 INSTRUCTIONS FOR LENALIDOMIDE DOSE MODIFICATIONS OR INTERRUPTION DURING A CYCLE.

Table 8: Dose Modification for Lenalidomide		
NCI CTC Toxicity Grade	Day 2-14 of Cycle	≥Day 15 of Cycle
Grade 3 neutropenia associated with fever (temperature $\geq 38.5^{\circ} \text{C}$) or Grade 4 neutropenia	
 • Hold (interrupt dose). • Follow CBC weekly. • If neutropenia has resolved to \leq grade 2 restart at next lower dose level and continue the cycle until Day 21. 	
 • Omit lenalidomide for remainder of cycle 
If neutropenia is the only toxicity for which a dose reduction is required. G-CSF may be used and the dose maintained for the next cycle at the investigators discretion.

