11.1 STATISTICAL/STUDY DESIGN

11.1.1 Phase I

The primary objective of the phase I part of the study is to determine the maximum tolerated dose (MTD) of lenalidomide when given in combination with obinutuzumab for subsequent testing in the phase II part of the trial. There are three predefined dose levels for lenalidomide (10 mg, 15 mg, 20 mg) with a fixed dose of obinutuzumab (1000mg) as outlined in Table 2.

Dose limiting toxicity (DLT) will be assessed during the first course of each cohort (28 days), and refers to a medically significant event which meets one of the following criteria using National Cancer Institute Common Terminology Criteria for Adverse Events (NCI CTCAE) version 4:

- Grade 3 or higher non-hematologic AE which is felt to be related to the study drug by the investigator with the exception of the following:
- Transient grade 3 or more infusion reaction that completely resolves within 24 hours.
- Grade 4 hematologic toxicity (Platelet count is defined as <25,000 for the purposes of determining DLT).
- Grade 3 neutropenia with elevated temperature (defined as >= 101 degrees F to be confirmed on two occasions).
- Grade 3 thrombocytopenia with bleeding.
- Treatment delay of greater than 2 weeks due to treatment related toxicity.

The target rate of DLT is 30%. The standard '3+3' design will be used. Applying the 3+3 design, the first cohort of 3 patients will be treated at dose level 1 and evaluated at the end of 28 days. The algorithm is as follows: (1) If 0 out of 3 patients experiences DLT, the next cohort of 3 patients will be

~~2013-0261: Obinutuzumab Plus Lenalidomide in Low Grade Lymphoma~~

treated at the next higher dose level. (2) If 1 out of 3 patients develop DLT, additional 3 patients will be treated at the same dose level. If no more DLT develops at the dose, i.e. 1 out of a total of 6 patients develops DLT, the dose escalation continues for the next cohort of 3 patients. (3) At any given dose, if greater than 1 out 3 patients or 1 out of 6 patients experience DLT, the dose level exceeds the MTD and 3 more patients will be treated at the next lower dose if there are less than 6 patients already treated at that dose. Following the above scheme, MTD is defined as the highest dose level in which 6 patients have been treated with less than 2 instances of DLT. Given 3 dose levels, it is anticipated that up to 18 eligible patients are required for the phase I part of the study.

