11.1.2 Phase II

The primary objective for the phase II part is to further evaluate the safety and efficacy of lenalidomide when given in combination with obinutuzumab at the MTD of lenalidomide determined in phase I. The maximum number of patients that will be recruited for the phase II part is 60 (include additional 54 and the 6 patients treated at the MTD in phase I) with 30 for each of the two patient cohorts: the patients with follicular lymphoma (grade 1-3a) and the patients with either follicular lymphoma, marginal zone lymphoma or SLL. The patients who are treated at the MTD in the phase I part will be included in phase II (in relevant cohort). The objective response (complete response + partial response) after 6 cycles and DLT after 1 cycle will be monitored simultaneously using the Bayesian approach of Thall, Simon, Estey (1995, 1996) as extended by Thall and Sung (1998).

Cohort A: Patients with Follicular lymphoma

Historical data on 43 patients (Witzig, 2009) with relapsed or refractory indolent non-Hodgkin's lymphoma treated with lenalidomide show an objective response (OR) rate of 23% and DLT rate of under 30%. Independence was assumed between OR and DLT. It is expected for the current trial that the two-drug combination will improve the OR rate by 20% to 43% while the DLT rate is maintained at or below 30%. A sample size of 30 patients ensures that, if the trial is not terminated early, a posterior 90% credible interval for OR rate will have width of 0.283 at most, under the assumption of a 43% of OR rate. We will claim that the regimen is worth of further investigation if the lower limit of the posterior 90% credible interval for OR rate is higher than 0.23. The probabilities of OR and DLT for the historical data are modeled by beta distributions (*Beta* (9.89, 33.11) and *Beta* (12.9, 30.1), respectively). The prior probabilities of OR and DLT for the experimental regimen are also modeled by beta distributions (*Beta* (0.46, 1.54) and *Beta* (0.6, 1.4), respectively), which have the same *means* as the corresponding beta distributions for the historical data.

Denoting the historical probabilities of objective response rate and DLT rate by $\{p(\text{OR}, \text{H}), p(\text{DLT}, \text{H})\}$, the following decision criteria will be applied:

- 1) Let E correspond to the experimental treatment, stop if

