Denoting the historical probabilities of objective response rate and DLT rate by $\{p(\text{OR}, \text{H}), p(\text{DLT}, \text{H})\}$, the following decision criteria will be applied:

- 1) Let E correspond to the experimental treatment, stop if
 $\text{Prob}\{p(\text{OR}, \text{H}) + \delta_{\text{OR}} > p(\text{OR}, \text{E}) \mid \text{data}\} > 0.95$, where $\delta_{\text{CR}} = 0.2$
- 2) Stop if $\text{Prob}\{p(\text{DLT}, \text{H}) + \delta_{\text{DLT}} < p(\text{DLT}, \text{E}) \mid \text{data}\} > 0.95$, where $\delta_{\text{DLT}} = 0$

Patients will be monitored in cohorts of 10 according to the following stopping boundaries for overall response and DLT.

Number of patients evaluated	Recommend stopping if \leq OR observed	Recommend stopping if \geq DLT observed
10	2	7
20	6	11
30	9	15

The operating characteristics are summarized in the following table (based on simulations from 10,000 trials).

True DLT Rate	True OR Rate	Prob(stop the trial early)
0.10	0.30	0.6491
	0.40	0.3014
	0.50	0.0889
	0.60	0.0164
	0.70	0.0018
0.20	0.30	0.6496
	0.40	0.3023
	0.50	0.0901
	0.60	0.0176
	0.70	0.0031
0.30	0.30	0.6574
	0.40	0.3179
	0.50	0.1104
	0.60	0.0395
	0.70	0.0253

0.40	0.30	0.7002
	0.40	0.4031
	0.50	0.2216
	0.60	0.1596
	0.70	0.1471
0.50	0.30	0.8016
	0.40	0.6050
	0.50	0.4848
	0.60	0.4438
	0.70	0.4355

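### If the MTD is 15 or 20 mg, the Cohort B toxicity boundary scores SLL patients in cycle 1 only, before they can reach the MTD

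*Combined protocol and SAP*

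**What the plan says.** **SLL dosing.** Section 5.2.1 states: "Patients with a diagnosis of small lymphocytic lymphoma (SLL) will begin cycle #1 at a maximum dose of 10 mg total daily". It continues: "This dose will be escalated by 5mg with each cycle up to the MTD if no toxicity is encountered". Table 7 in Section 6.2 agrees, giving the SLL starting dose as "MTD or max of 10 mg daily for 21 days every 28 days". Phase II patients with follicular lymphoma (FL) or marginal zone lymphoma (MZL) start at the MTD.

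**Possible MTDs.** Section 11.1.1: "There are three predefined dose levels for lenalidomide (10 mg, 15 mg, 20 mg". Table 1 adds a 5 mg level below these.

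**Phase I population.** Section 3.2: "Patients with SLL/CLL will be excluded during the phase I portion of the study".

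**DLT window.** Section 11.1.1: "Dose limiting toxicity (DLT) will be assessed during the first course of each cohort (28 days". For phase II, Section 11.1.2 says response after six cycles and "DLT after 1 cycle will be monitored simultaneously". No later or moving window is given for SLL.

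**Cohort B rule.** Cohort B pools FL, MZL and SLL, with no SLL quota or cap. "Patients will be monitored in cohorts of 10 according to the following stopping boundaries for overall response and DLT": stop at 7 or more DLTs in 10, 11 in 20, or 15 in 30. The same section sets the phase II aim as safety and efficacy at the MTD found in phase I.

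**The concern.** The dose schedule and the DLT window do not fit together for SLL. The boundary is meant to protect against excess toxicity at the MTD. With an MTD above 10 mg, each SLL patient is scored while still below it, and the first cycle at the MTD falls after scoring has closed. Phase I cannot fill the gap because SLL is excluded from it.

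Two things are at stake. First, no formal DLT assessment of SLL exists at an MTD of 15 or 20 mg, although the protocol's own lower start treats SLL as different. Second, each SLL patient scored at 10 mg or less fills one of the 10, 20 or 30 places in the Cohort B denominator. This weakens the rule for the FL and MZL patients who are at the MTD. The Cohort B operating-characteristics table gives each row a single DLT rate for all patients, so it does not show this.

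**Working it through.** **1. When SLL reaches the MTD.** Start at 10 mg and add 5 mg per cycle, so for an MTD of 10 mg or more the earliest cycle at the MTD is 1 + (MTD − 10)/5.
- MTD 10 mg: cycle 1. (At 5 mg, also cycle 1, since Table 7 starts at the MTD.)
- MTD 15 mg: cycle 2.
- MTD 20 mg: cycle 3.

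The DLT window closes at the end of cycle 1.

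**2. Reproducing the plan's boundary and table.** Inputs from Section 11.1.2, Cohort B: historical DLT Beta(13.2, 30.8), prior Beta(0.6, 1.4), margin 0, stop if the posterior probability exceeds 0.95. With x DLTs in n, the posterior is Beta(0.6 + x, 1.4 + n − x). The probability that it exceeds the historical rate is:
- n = 10: 0.944 at 6 DLTs, 0.983 at 7.
- n = 20: 0.926 at 10, 0.964 at 11.
- n = 30: 0.920 at 14, 0.953 at 15.

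This gives 7, 11 and 15, as stated.

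For a common DLT rate p, the chance that the DLT rule alone stops at 10 or 20 patients is

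T(p) = P(X₁₀ ≥ 7) + Σ over x = 0 to 6 of P(X₁₀ = x) · P(X′₁₀ ≥ 11 − x),

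where X₁₀ and X′₁₀ are the DLT counts in the first and second ten patients.
- T(0.30) = 0.011 + 0.013 = 0.024
- T(0.40) = 0.055 + 0.091 = 0.146
- T(0.50) = 0.172 + 0.263 = 0.435

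With response independent of DLT, overall early stopping is 1 − (1 − T)(1 − R). At a true response rate of 0.50, R = 0.0889, which is the plan's entry at DLT 0.10, where T is about 0.
- DLT 0.50: 1 − 0.5654 × 0.9111 = 0.4848. The plan gives 0.4848.
- DLT 0.30: 1 − 0.9764 × 0.9111 = 0.1104. The plan gives 0.1104.

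All 25 Cohort B entries reproduce to within 0.0001 when stops at 10 and 20 are counted. So the table rests on one DLT rate for every patient.

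**3. Effect of scoring SLL at 10 mg.** Let s be the SLL share and d the DLT rate at 10 mg, with 50% at the MTD. The rate the rule sees is m = s·d + (1 − s)·0.50. The values of s, d and 50% are assumptions, since the documents give none of them.

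| SLL share | m, d = 10% | T(m) | m, d = 20% | T(m) |
|---|---|---|---|---|
| 0 | 0.500 | 0.435 | 0.500 | 0.435 |
| 10% | 0.460 | 0.302 | 0.470 | 0.333 |
| 20% | 0.420 | 0.191 | 0.440 | 0.243 |
| one third | 0.367 | 0.087 | 0.400 | 0.146 |
| half | 0.300 | 0.024 | 0.350 | 0.065 |

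Fixing the mix in each block of 10, instead of letting it vary, gives similar results: 0.085 and 0.154 with three SLL patients, 0.011 and 0.053 with five.

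**4. Why accumulating DLTs over cycles is not the answer.** Suppose SLL DLTs were counted from cycle 1 through the first MTD cycle against the existing boundary, at a constant 30% per cycle, the rate the plan tolerates.
- Two cycles: 1 − 0.7² = 0.51. At one third SLL, m = 0.370 and T = 0.09. At half, m = 0.405 and T = 0.16.
- Three cycles: 1 − 0.7³ = 0.657. At one third SLL, m = 0.419 and T = 0.19. At half, m = 0.4785 and T = 0.36.

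False stopping should be 0.024.

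**The case against.** The other side has several fair points.

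- **The gap depends on phase I.** At an MTD of 10 mg or lower it does not arise. This stands.
- **A 50% rate in all histologies is severe.** Phase I accepts an MTD only with fewer than 2 DLTs in 6, and at a true 50% rate the chance of at most 1 in 6 is 7/64 = 0.11. Cohort A also applies 7/11/15 to FL patients at the MTD from cycle 1, so toxicity common to all histologies is still monitored there at full strength (0.43). This stands. What depends on Cohort B is toxicity particular to SLL or MZL.
- **The SLL share may be small.** Nothing fixes it, and at 10% the loss is modest.
- **Cycle-1 DLT with step-up dosing measures the regimen as given.** This is true of the starting step. But Section 11.1.2 says that phase II evaluates safety at the MTD, and the SLL scoring does not.

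A reader might infer that SLL patients at the MTD go unmonitored, or that the Cohort B rule is blind to the MTD. The documents support neither. Escalation requires absence of toxicity (Section 5.2.1). Holds and reductions apply in every cycle (Sections 6.2.1 and 6.2.2), and adverse events are evaluated at each visit (Section 6). Serious events go to the IND Office within 5 working days, or within 24 hours if fatal or life-threatening, unexpected and related (Section 12.1.2). Section 11.2 tabulates toxicity by cohort with no cycle-1 limit. FL and MZL patients in Cohort B are scored at the MTD, so the rule is diluted, not empty. What is missing is narrower: none of these safeguards feeds a stopping boundary for SLL at the MTD.

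**Conclusion.** The point holds on condition that the MTD is 15 or 20 mg, the two higher of the three planned levels. No SLL cycle at the MTD then enters any DLT rule in phase I or phase II, and the Cohort B count is diluted in proportion to the SLL share. That much follows directly from the text.

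The size is less certain. Stopping falls from 0.43 to between 0.30–0.33 (10% SLL) and 0.02–0.07 (half SLL), but only under the assumed rates of 50% at the MTD and 10–20% at 10 mg. These figures illustrate the loss and do not predict it. The change should be made. The point does not call the SLL dose schedule into question, and it does not show that the primary safety objective fails, because that objective does not rest on the DLT boundary alone.

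**What to change.** Leave the dose schedule unchanged and reconcile the DLT window with it in Section 11.1.2.

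1. For the Cohort B boundary, score each SLL patient over one 28-day cycle: the first at the MTD, or at the highest dose reached. Count a patient whose DLT at a lower step prevents escalation as a DLT. Count the patient as evaluated only once this is known.
2. Rerun the Cohort B operating characteristics with a stated SLL share, or a range, and an SLL per-patient DLT rate that includes events at the lower steps. Adjust the boundary if false stopping is no longer acceptable.
3. Do not apply the current one-cycle boundary to DLTs accumulated over two or three cycles.
4. Report Cohort B DLT by histology and by dose at the time of the event.

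Cost: protocol wording and a recomputed 25-row table. No new visits are needed, because day 1 and day 14 hematology is already scheduled in cycles 2–12 (Section 2.1, note 11) and adverse events are reviewed at each visit. SLL patients become evaluable for DLT one or two cycles later, which may delay a toxicity look. That is still well before their six-cycle response is known.
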